Appendix III

PCS Criteria

PCS Criteria

Table 1 PCS Criteria for Clinical Safety Laboratory Tests

Laboratory Test	CDISC Term	Unit	PCS Low	PCS High
Haematology / Coagulation				
B-haemoglobin	HGB	g/L	≤ 95 (women) ≤ 115 (men)	≥ 165 (women) ≥ 185 (men)
B-erythrocytes (red cell count)	RBC	x 10E12/L	≤ 3.5 (women) ≤ 3.8 (men)	≥ 6.0 (women) ≥ 7.0 (men)
B-haematocrit (packed cell volume)	HCT	V/V	≤ 0.32 (women)	≥ 0.50 (women)
			≤ 0.37 (men)	≥ 0.55 (men)
B-MCV (mean cell volume)	MCV	fL	≤ 0.8 x LLN	≥ 1.2 x ULN
B-total leucocyte (white cell count)	WBC	x 10E9/L	≤ 2.8	≥ 16
B-neutrophils/leucocytes	NEUTLE	%	≤ 20	≥ 85
B-eosinophils/leucocytes	EOSLE	%		≥ 10
B-basophils/leucocytes	BASOLE	%		≥ 10
B-lymphocytes/leucocytes	LYMLE	%	≤ 10	≥ 75
B-monocytes/leucocytes	MONOLE	%		≥ 15
B-thrombocytes (platelet count)	PLAT	x 10E9/L	≤ 75	≥ 600
P-INR (prothrombin ratio)	INR	Ratio		≥ 2.0
B-prothrombin time	PT	Sec		≥ 18
Liver				
S-aspartate aminotransferase	AST	I/L		≥ 3 × ULN
S-alanine aminotransferase	ALT	I/L		≥ 3 × ULN
S-bilirubin	BILI	µmol/L		≥ 34
S-bilirubin, direct	BILDIR	µmol/L		≥ 12
S-bilirubin, indirect	BILIND	µmol/L		≥ 22
S-alkaline phosphatase	ALP	I/L		≥ 3 × ULN
S-gamma glutamyl transferase	GGT	I/L		≥ 200
S-alpha-glutathione S-transferase (alpha-GST)	GSTAL	µg/L		≥ 20
Kidney				
S-creatinine	CREAT	µmol/L		≥ 1.5 × ULN
B-urea nitrogen (BUN)	BUN	mmol/L		≥ 11
S-uric acid (urate)	URATE	µmol/L		≥ 510 (women) ≥ 630 (men)
Electrolytes				
S-sodium (natrium)	SODIUM	mmol/L	≤ 125	≥ 155
S-potassium (kalium)	K	mmol/L	≤ 3.0	≥ 6.0

Laboratory Test	CDISC Term	Unit	PCS Low	PCS High
S-calcium	CA	mmol/L	≤ 1.8	≥ 3.0
S-chloride	CL	mmol/L	≤ 90	≥ 117
S-magnesium	MG	mmol/L	≤ 0.6	≥ 1.3
S-phosphate (phosphorus, (inorganic)	PHOS	mmol/L	≤ 0.65	≥ 1.95
S-bicarbonate	BICARB	mmol/L	≤ 12	≥ 38
Endocrine / Metabolic				
B-glucose, non-fasting/unknown	GLUC	mmol/L	≤ 3.4	≥ 9.4
B-glucose, fasting	GLUC	mmol/L	≤ 3.0	≥ 6.0
S-glucose, non-fasting/unknown	GLUC	mmol/L	≤ 3.9	≥ 11.1
S-glucose, fasting	GLUC	mmol/L	≤ 3.5	≥ 7.0
B-glycosylated haemoglobin, fasting	HBA1C	Hb fract.		≥ 6.5
S-prolactin	PROLCTN	mIU/L		≥ 1350
S-thyrotropin/TSH	TSH	mIU/L	≤ 0.3	≥ 5.5
S-protein (total)	PROT	g/L	≤ 45	≥ 95
S-albumin	ALB	g/L	≤ 27	
Lipids				
S-cholesterol total, non-fasting/unknown	CHOL	mmol/L		≥ 7.8
S-cholesterol total, fasting	CHOL	mmol/L		≥ 6.2
S-triglycerides, non-fasting/unknown	TRIG	mmol/L		≥ 5.65
S-triglycerides, fasting	TRIG	mmol/L		≥ 4.2
S-LDL cholesterol, non-fasting/unknown	LDL	mmol/L		≥ 5.3
S-LDL cholesterol, fasting	LDL	mmol/L		≥ 4.9
S-HDL cholesterol, non-fasting/unknown	HDL	mmol/L	≤ 0.8	
S-HDL cholesterol, fasting	HDL	mmol/L	≤ 0.9	
Cardiac/Skeletal/Muscle				
S-creatine kinase (total)	CK	I/L		≥ 400 (women) ≥ 750 (men)
S-creatine kinase MB isoenzyme	CKMB	µg/L		≥ 8.5 or
	CKMBCK	%		≥ 3.5% of total CK
S-lactate dehydrogenase (total)	LDH	IU/L		≥ 750
S-troponin I	TROPONI	µg/L		≥ 1.5
S-troponin T	TROPONT	µg/L		≥ 0.4
Infection				
S-C-reactive protein	CRP	mg/L		≥ 25
S-globulin (total)	GLOBUL	g/L	≤ 15	≥ 55

Laboratory Test	CDISC Term	Unit	PCS Low	PCS High
Urine				
Urinary pH	PH		≤ 4	≥ 9
S=serum; B=whole blood; U=urine				

Table 2 PCS Criteria for Vital Signs, Weight/BMI, and Waist Circumference

Variable	CDISC Term	Unit	PCS Low	PCS High
Waist circumference	WSTCIR	Cm	decrease ≥ 7%	increase ≥ 7%
Weight	WEIGHT	Kg	decrease ≥ 7%	increase ≥ 7%
Body Mass Index	BMI	kg/m ²	decrease ≥ 7%	increase ≥ 7%
Pulse rate, supine/sitting/unknown	PULSE	beats/min	< 50 and decrease ≥ 15	≥ 120 and increase ≥ 15
Diastolic blood pressure, supine/sitting/unknown	DIABP	mmHg	≤ 50 and decrease ≥ 15	≥ 105 and increase ≥ 15
Systolic blood pressure, supine/sitting/unknown	SYSBP	mmHg	≤ 90 and decrease ≥ 20	≥ 180 and increase ≥ 20
Orthostatic systolic blood pressure	OBP	mmHg	≤ -30	
Orthostatic pulse rate	OPR	beats/min		≥ 20
Temperature	TEMP	°C	decrease ≥ 2	≥ 38.3 and increase ≥ 2

Increase/decrease is relative to the baseline value.

Table 3 PCS Criteria for ECG Parameters

ECG Parameter	CDISC Term	Unit	PCS Low	PCS High
Absolute Time Interval				
PR interval	PRMEAN	Msec		≥ 260
QRS interval	QRSDUR	Msec		≥ 150
QT interval	QTMEAN	Msec		≥ 500
Derived Time Interval				
Heart rate	HRMEAN	beats/min	< 50 and decrease ≥ 15	≥ 120 and increase ≥ 15
QTcB interval	QTCB	Msec	< 300	> 500 or increase > 60
QTcF interval	QTCF	Msec	< 300	> 500 or increase > 60

Increase/decrease is relative to the baseline value.

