9.6.2 Clinical Safety Laboratory Tests

The clinical safety laboratory tests are listed in [Panel 5](#).

Panel 5 Clinical Safety Laboratory Tests

Haematology B-haemoglobin [HGB] B-erythrocyte count [RBC] B-total leucocyte count [WBC] B-neutrophils ^a [NEUTLE] B-eosinophils ^a [EOSLE] B-basophils ^a [BASOLE] B-lymphocytes ^a [LYMLE] B-monocytes ^a [MONOLE] B-thrombocyte count [PLAT] B-haematocrit [HCT] P-prothrombin time [PT]	Liver^b S-total bilirubin [BILI] S-conjugated bilirubin [BILDIR] S-alkaline phosphatase [ALP] S-alanine aminotransferase [ALT] S-aspartate aminotransferase [AST] S-gamma-glutamyl transferase [GGT]	Infection^c S-C-reactive protein [CRP] Immune response lab kit^e P-histamine [HISTAMINE] S-tryptase [TRYPTASE] immunoglobulin E [IgE] complement C3, C4 [C3 and C4]
Electrolytes^b S-sodium [SODIUM] S-potassium [K] S-calcium (total) [CA]	Kidney^b S-creatinine [CREAT] S-urea nitrogen [UREAN]	Urine^f U-protein (dipstick) [PROT] U-glucose (dipstick) [GLUC] U-blood (dipstick) [OCCBLD] Urine drug screen ^c
Endocrine and Metabolic^b S-albumin [ALB] S-glucose ^d [GLUC] B-HbA1c [HBA1C] S-creatinine phosphokinase [CK]	Lipids^{b,d} S-low density lipoprotein [LDL] S-high density lipoprotein [HDL] S-triglycerides [TRIG] S-cholesterol (total) [CHOL]	Pregnancy^g S-hCG ^h [HCG] Urine (dipstick)

B = blood; P = plasma; S = serum; U = urine

a Count and % of total leucocytes

b Clinical chemistry

c Performed at the Screening Visit only

d Fasting, when possible

e Performed per investigator judgement, see section 10.1.3.

f If urine dipstick is positive, a urine microscopic panel will be conducted

g Only for women of childbearing potential

h Performed at Screening Visit and Safety Follow-Up Visit only

Blood and urine samples for the clinical safety laboratory tests will be collected as outlined in [Panel 2](#).

The blood and urine sampling and handling procedures are described in the study-specific *Laboratory Specification Manual*.

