4 COVID-19

For this trial, all participants are considered to have been enrolled after the beginning of the COVID-19 outbreak.

The following information is collected with regards to COVID-19:

- Whether a visit was done remotely due to COVID-19 including which assessments were/were not performed
- Whether participants withdrew due to the COVID-19 situation
- Whether participants got diagnosed with COVID-19

Remotely done visits will be tabulated or listed as appropriate. Participants diagnosed or withdrawn due to COVID-19 will be seen from tables/listings of AEs and AEs leading to withdrawal respectively.

5 Endpoints

The endpoints are summarized in [Panel 2](#). There are no key secondary endpoints in this trial.

Panel 2 Endpoints

Objectives	Endpoints
Primary Objective 
 To evaluate the long-term safety and tolerability of eptinezumab in participants with chronic cluster headache (cCH) 	
 Primary endpoints: 
 - adverse events - absolute values and changes from Baseline in clinical safety laboratory test values, vital signs, weight, and electrocardiogram (ECG) parameter values - potentially clinically significant (PCS) clinical safety laboratory test values, vital signs, weight changes, and ECG parameter values - development of specific anti-eptinezumab antibodies (ADAs) including neutralizing antibodies (NABs) - Columbia-Suicide Severity Rating Scale (C-SSRS) score

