14.2 General Methodology for Other Safety Data

Unless otherwise specified, tables, graphs, and listings will be based on the APTS.

The denominators for the summaries of a given variable will be based on the number of participants with non-missing values at a given visit or during the assessment period.

Descriptive statistics for the safety variables, both absolute values and changes from Baseline, will be presented by visit.

The number and percentage of participants with at least one PCS value at any post-baseline assessment time point will be summarized by variable. All available assessments will be included in the evaluation of PCS values.

For participants with post-baseline PCS values, listings will be provided including all the values for those participants for the variable, with flagging of PCS values and out-of-reference-range values.

All the adverse events in participants with post-baseline PCS values will be listed by participant screening number; the listing will include the PCS value, the assessment date, the change from Baseline in PCS value, the preferred term for the adverse event, and start date and stop date of the adverse event. The PCS values and adverse events will be listed in chronological order according to assessment date and the start date of the adverse event.

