14.3 Clinical Safety Laboratory Test Data

14.3.1 Data Presentation

The PCS criteria used for the clinical safety laboratory are the Lundbeck standard PCS criteria described in SOP_09978: *GPV – PCS and standard reference values for laboratory investigations, vital signs and ECGs in clinical studies*, version 6, and are also included in [Table 2](#).

The clinical safety laboratory test values will be presented in both conventional and Système International (SI) units.

Fasting lipid and fasting glucose concentrations will be presented in separate tables from the overall laboratory tables.

For urine dipsticks, for which the results are categorical values (for example, negative, trace, 1+, 2+), the number and percentage of participants will be summarized by visit for each test.

The microscopy results will be listed by assessment time point for participants with findings.

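### The only HbA1c PCS limit (≥ 6.5) cannot be reached in its printed unit, a haemoglobin fraction, and covers fasting samples only

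*SAP*

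**What the plan says.** SAP Appendix III, Table 1 lists the laboratory PCS criteria. Its single HbA1c row is labelled "B-glycosylated haemoglobin, fasting", carries the code HBA1C and the unit Hb fract., has no low limit, and has a high limit of ≥ 6.5. Glucose and each of the lipids have two kinds of row, one for fasting samples and one for the rest, for example "S-glucose, non-fasting/unknown".

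Protocol 9.6.2, Panel 5 includes HbA1c among the safety laboratory tests. The fasting footnote in that panel is attached to serum glucose and to the lipids, not to HbA1c, and it asks only for "Fasting, when possible". SAP 14.3.1 makes the same division: "Fasting lipid and fasting glucose concentrations will be presented in separate tables from the overall laboratory tables". HbA1c is not named there.

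SAP chapter 5, Panel 2 puts "potentially clinically significant (PCS) clinical safety laboratory test values, vital signs, weight changes, and ECG parameter values" among the primary endpoints. SAP 14.2 gives the analysis: "The number and percentage of participants with at least one PCS value at any post-baseline assessment time point will be summarized by variable". The same section brings all available assessments into the PCS evaluation. It also uses a post-baseline PCS value as the trigger for two listings: all of the participant's values for that variable, and the participant's adverse events alongside the PCS values. SAP 14.3.1 attributes the limits to version 6 of a sponsor SOP, which is not part of the documents.

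**The concern.** A PCS limit is a decision rule: it turns a measurement into a count in a primary safety table. The rule for HbA1c has two faults. The number and the unit contradict each other, so the text does not define which values count. And the rule is stated for fasting samples only, for a test that the protocol does not require to be taken fasting.

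If the row were implemented as printed, the HbA1c line in the PCS table would show zero whatever the data, and a reader would take that zero as reassurance. The PCS-triggered listings for HbA1c would be empty for the same reason. If the fasting qualifier were applied as printed, non-fasting or fasting-unknown samples would drop out of the evaluation, against the instruction in SAP 14.2 to use all assessments.

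**Working it through.** There is no derived figure to reproduce. The check is one of range, unit and coverage.

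**1. Can the limit be reached in its unit?**
- Inputs (SAP Table 1): limit 6.5, rule value ≥ 6.5, unit haemoglobin fraction.
- A fraction lies between 0 and 1. The largest possible value gives 1.0 ≥ 6.5, which is false.
- Selected values under both readings:

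| HbA1c (%) | As a fraction | Fraction ≥ 6.5? | Percent ≥ 6.5? |
|---|---|---|---|
| 4 | 0.04 | no | no |
| 6 | 0.06 | no | no |
| 6.5 | 0.065 | no | yes |
| 8 | 0.08 | no | yes |
| 15 | 0.15 | no | yes |
| 100 | 1.00 | no | yes |

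- If 6.5 is meant as a percentage, the equivalent fraction is 6.5 / 100 = 0.065. The printed limit would then be 6.5 / 0.065 = 100 times too large for its printed unit.

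**2. Does the table use fraction in some looser sense?** Its other entries suggest not. Haematocrit, in V/V, is written in decimals (women ≤ 0.32 and ≥ 0.50; men ≤ 0.37 and ≥ 0.55). The white-cell differentials are percentages and carry % in the unit column. So the table separates fractions from percentages elsewhere. Since % appears intact in those rows, a sign lost when the PDF was read is an unlikely explanation, though it cannot be fully excluded.

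**3. Which samples have a limit?** Rows in SAP Table 1 by fasting status:

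| Test | Fasting | Non-fasting/unknown |
|---|---|---|
| Glucose, blood | 1 | 1 |
| Glucose, serum | 1 | 1 |
| Cholesterol | 1 | 1 |
| Triglycerides | 1 | 1 |
| LDL | 1 | 1 |
| HDL | 1 | 1 |
| HbA1c | 1 | 0 |

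HbA1c is the only test with a fasting row and no counterpart. Panel 5 of the protocol and SAP 14.3.1 both leave it outside the fasting group, so the qualifier has no support in how the sample is collected or presented.

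**4. What depends on the row?** Under SAP 14.2: the number and percentage of participants with a PCS HbA1c value, and the two listings that such a value triggers. Not dependent on it: descriptive statistics for absolute values and changes from baseline by visit, and adverse event reporting.

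**5. Related labels.** SAP 14.3.1 directs the reader to Table 2 for the laboratory limits. Table 2 holds vital signs, weight and waist circumference; the laboratory limits are in Table 1. Separately, Panel 5 collects serum urea nitrogen (code UREAN), while Table 1 labels the row as blood, code BUN.

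**The case against.** The best reply is that this is a slip in a unit label. A limit of 6.5 is visibly not a fraction, a programmer would query it, and if results are held in percent and compared with 6.5 the flags work. The limits come from a standard SOP that may print the row correctly. Nothing in the SAP says that the fasting qualifier will be used to discard HbA1c samples. The proportion of non-fasting samples is unknown, and some HbA1c samples may well be fasting because glucose and lipids are drawn fasting where possible. Other safeguards remain: serum glucose has its own limits for both fasting states, investigators judge every out-of-range value, and clinically significant results are recorded as adverse events. All of this stands and bounds the impact. It does not repair the row, which still states a rule that cannot operate in its own unit.

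A reader might go further in four ways that the documents do not support.
- *The trial report will show zero HbA1c flags, or on some other scale will flag nearly everyone.* Either outcome depends on the unit in which results are stored and compared, and neither document gives it.
- *Presenting laboratory results in conventional and SI units means that the count will be driven by the unit.* SAP 14.3.1 describes presentation; it does not say which unit is used for flagging.
- *The intended limit is 0.065.* That is a plausible inference from 6.5%, but only the SOP can confirm it.
- *Urea nitrogen has no usable limit because the codes differ.* The SAP never says that limits are matched on code. Code alone could not work for glucose, where one code serves four rows of Table 1 and also urine glucose in Panel 5. Table 1 is a general list that includes tests not collected here, and prothrombin time also changes specimen prefix between the documents (plasma in Panel 5, blood in Table 1) under the same code. This is a label to harmonise, not a missing criterion.

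**Conclusion.** The point holds. The HbA1c limit and unit in SAP Table 1 contradict each other, and the row covers fasting samples only for a test that the protocol does not make a fasting test. Taken literally, the flag rate is zero for any data; on a percent reading, values of 6.5% or more are flagged. The text does not choose between the two, and how many participants would be misclassified cannot be estimated from the documents.

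The reach is small: one laboratory variable, its PCS count and its PCS-triggered listings. It would be too strong to say that the primary safety endpoint as a whole is compromised, because PCS values are tabulated separately by variable and the rest of the endpoint is untouched. The analysis is descriptive, so no formal test is affected, and the sample size does not depend on this limit. The conclusion assumes that Hb fract. means a 0-to-1 fraction, which the table's treatment of haematocrit and of percentages supports, and that the row has been read correctly from the PDF. It is worth correcting because the row feeds a named primary endpoint and costs almost nothing to put right.

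**What to change.** In SAP Appendix III, Table 1, check the HbA1c row against the sponsor's PCS SOP and:
- put limit and unit on one scale; if percent is meant, keep 6.5 and print the unit as % (the same limit as a fraction is 0.065);
- remove the fasting qualifier, or add a non-fasting/unknown row, as the SOP specifies, so that every available HbA1c assessment has a criterion, as SAP 14.2 requires.

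Confirm that the analysis program compares HbA1c with the limit in the unit finally printed.

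As minor harmonisation in the same edit, align the urea nitrogen label with the analyte collected (serum, UREAN), confirming with the SOP that the limit applies to serum, and change the SAP 14.3.1 pointer for laboratory limits from Table 2 to Table 1.

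The cost is one corrected table row, possibly one added row, and two label corrections. No new data, visits or analyses are needed.

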Appendix IV

Trial flow chart

Trial flow chart

Table 4 Trial Procedures and Assessments

Visit Name	Screening Period															Withdrawal ^d
Visit Number	1 ^{a, z}	2 ^a	3 ^b	4 ^b	5 ^a	6 ^b	7 ^b	8 ^a	9 ^b	10 ^b	11 ^a	12 ^b	13 ^b	14 ^a	15 ^a	WD ^a
End of Week	-4	0	4	8	12	16	20	24	28	32	36	40	44	48	56	
Visit Window ^e (days relative to nominal visit)		+3	±3	±3	±3	±3	±3	±3	±3	±3	±3	±3	±3	±3	±3	
Screening and Baseline Procedures and Assessments																
Signed informed consent(s) ^{f, z}	√															
Demographics (age, sex, race)	√															
Diagnosis	√															
Disease-specific history ^g	√															
Relevant history (social, medical, psychiatric, neurological)	√															
Previous cluster headache abortive, transitional and preventive therapy use ^g	√															
Recent medication (past 3 months)	√															
Substance use (for example smoking and alcohol)	√															
Height	√															
Family history of cluster headache	√															
Urine drug screen	√															
Inclusion/exclusion criteria	√	√														
Efficacy Assessments (ePROs) ^{h, i}																
eDiary recording ^{j, k}	√	√	√	√	√	√	√	√	√	√	√	√	√	√	√	
eDiary compliance check ^l	√	√	√	√	√	√	√	√	√	√	√	√	√	√	√	
PGIC ^k			√	√	√	√	√	√	√	√	√	√	√	√	√	√

Visit Name	Screening Period															Withdrawal ^d
Visit Number	1 ^{a, z}	2 ^a	3 ^b	4 ^b	5 ^a	6 ^b	7 ^b	8 ^a	9 ^b	10 ^b	11 ^a	12 ^b	13 ^b	14 ^a	15 ^a	WD ^a
End of Week	-4	0	4	8	12	16	20	24	28	32	36	40	44	48	56	
Visit Window ^e (days relative to nominal visit)		+3	±3	±3	±3	±3	±3	±3	±3	±3	±3	±3	±3	±3	+3	
SIS ^k		✓	✓		✓	✓		✓	✓		✓	✓		✓		✓
Pharmacoeconomic Assessments (ePROs) ^{h, i}																
EQ-5D-5L ^k		✓	✓			✓			✓			✓		✓		✓
HCRU ^k		✓	✓			✓			✓			✓		✓		✓
WPAI:GH2.0 ^k		✓	✓			✓			✓			✓		✓		✓
Pharmacokinetic Assessments																
Blood sampling for exploratory eptinezumab quantification ^{m, s}		✓				✓			✓			✓		✓	✓	✓
Pharmacodynamic Assessments (exploratory biomarkers)																
Blood sampling for pharmacodynamic/exploratory biomarkers ^{m, s}		✓				✓			✓			✓		✓		✓
Safety Assessments																
Adverse events ^{n, o, y}	✓	✓	✓	✓	✓	✓	✓	✓	✓	✓	✓	✓	✓	✓	✓	✓
Blood and urine sampling for clinical safety laboratory tests ⁿ	✓	✓			✓			✓			✓			✓	✓	✓
Blood sampling for ADA including NAbs ^{n, u}		✓			✓			✓			✓			✓	✓	✓
Vital signs ^{n, o} (including body temperature), weight	✓	✓			✓			✓			✓			✓	✓	✓
ECG ⁿ	✓	✓			✓			✓			✓			✓	✓	✓
Examinations (physical, neurological) ^p	✓	✓			✓			✓			✓			✓	✓	✓
C-SSRS ^{n, q}	✓	✓			✓			✓			✓			✓	✓	✓
Biobanking ^r																
Blood sampling for gene expression profiling (RNA) ^s		✓							✓					✓		

Visit Name	Screening Period															Withdrawal ^d
Visit Number	1 ^{a, z}	2 ^a	3 ^b	4 ^b	5 ^a	6 ^b	7 ^b	8 ^a	9 ^b	10 ^b	11 ^a	12 ^b	13 ^b	14 ^a	15 ^a	WD ^a
End of Week	-4	0	4	8	12	16	20	24	28	32	36	40	44	48	56	
Visit Window ^e (days relative to nominal visit)		+3	±3	±3	±3	±3	±3	±3	±3	±3	±3	±3	±3	±3	±3	+3
Blood sampling for metabolomics/proteomics (plasma) ^s		√						√							√	
Blood sampling for pharmacogenetics (DNA) (optional) ^t		√														
Blood sampling for possible future ADA assessment ^u		√			√			√			√			√	√	

Other Trial Procedures and Assessments

IMP administered (IV infusion) ^v		√			√			√			√					
IMP accountability		√			√			√			√					
Concomitant medication (prescription and non-prescription) ⁿ	√	√	√	√	√	√	√	√	√	√	√	√	√	√	√	√
eDiary training ⁱ	√															
ePRO training ⁱ	√															
eDiary closeout ^w														√	√	
Pregnancy test ^{n, x}	√	√			√			√			√			√	√	

ADA = anti-drug antibody; C-SSRS = Columbia-Suicide Severity Rating Scale; DNA = deoxyribonucleic acid; ECG = electrocardiogram; EQ-5D-5L = EuroQol 5-Dimension 5-Level; HCRU = Health Care Resources Utilization; IMP = investigational medicinal product; IV = intravenous; NAbs = neutralizing antibodies; PGIC = Patient Global Impression of Change; ePRO = electronic participant-reported outcome; RNA = ribonucleic acid; SIS = Sleep Impact Scale; WD = Withdrawal; WPAI:GH2.0 = Work Productivity Activity Impairment: General Health second version.

- a This visit should be a site visit.
- b For phone visits, the participant will be contacted for eDiary compliance check, to ensure that the selected assessments have been completed and for collection of relevant information such as adverse events and concomitant medications.
- c The SFU Visit should be scheduled 20 weeks (5 half-lives) after the last eptinezumab administration.
- d Participants who withdraw from study, except for those who withdraw their consent, will be asked to attend a Withdrawal Visit as soon as possible.
- e If the date of a clinic visit or phone contact does not conform to the schedule, subsequent visits should be

planned to maintain the visit schedule relative to the Baseline Visit (Day 0/Visit 2).

- f At the Screening Visit, the participant will be asked to sign the main Informed Consent Form (ICF), and the ICF for blood sampling for pharmacogenetics (optional). Depending of the country requirements, the number of ICFs may be different. Under exceptional circumstances, the discussion with the participants about the Informed Consent Form(s) can be done as a virtual clinic visit and the Informed Consent Form(s) can be provided remotely in line with the US FDA and EMA guidances. According to the EMA guidance, this could comprise contacting the participants via phone or video-calls and obtaining oral consents, to be documented in the participants' medical records, supplemented with email confirmation. Any consent obtained this way should be documented and confirmed by way of normal consent procedures at the earliest opportunity when the participants are back at the clinical sites.
- g Participants must have adequately documented records or reliable history of cCH and previous treatment for cCH within the 12 months prior to the Screening Visit. See protocol (section 12) for definition of adequately documented records.
- h During the Treatment Period, ePROs which are scheduled in alignment with a clinic visit can be completed in the clinic or in the remote setting within 3 days prior to the scheduled clinic visit date. ePROs which are scheduled in alignment with a phone contact must be completed in the remote setting and can be completed on the day or within 3 days prior to the scheduled phone contact date.
- i At the Screening Visit, the participant must be assisted with the provisioning and training of the eDiary and ePROs. Details will be provided in a separate training module.
- j Participants must complete the eDiary daily during the Screening Period (from Week -4 to Day 0) and during the first 4 weeks that follow each eptinezumab infusion (Weeks 1 to 4, 13 to 16, 25 to 28, and 37 to 40) and weekly for Weeks 5 to 12, 17 to 24, 29 to 36, and 41 to 48.
- k Participants must complete the daily eDiary and ePRO entries prior to infusion and prior to any interaction with the clinical site staff.
- l In addition to the eDiary compliance checks performed at the defined trial visits, ongoing evaluation of eDiary compliance will be performed by the clinical site (based on eDiary reporting) and more frequent contact with participants may be performed in case of non-compliance.
- m At IMP Visits, two blood samples will be collected for exploratory eptinezumab quantification and exploratory biomarkers – one sample prior to the eptinezumab infusion and one sample 1 hour after the end of the infusion.
- n Infusion must be preceded by the assessment of vital signs (including body temperature), weight, concomitant medications, adverse events, ECG, blood sampling (for clinical safety laboratory tests, exploratory eptinezumab quantification, ADA including NAb, and exploratory biomarkers), urine sampling (for clinical safety laboratory and pregnancy tests) and C-SSRS. Vital signs must be assessed prior to blood sampling.
- o Vital signs (including body temperature) and adverse events must be checked both prior to and after infusion. Vital signs must be assessed prior to blood sampling.
- p Physical and neurological examinations for all clinic visits after the Screening Visit are to be conducted at the discretion of the investigator. If these examinations are conducted at an IMP Visit, these must be performed prior to the infusion.
- q C-SSRS will be administered by the authorised rater at the clinic.
- r Biobank may be excluded or optional per local regulation.
- s Exploratory gene expression profiling (ribonucleic acid [RNA]) and metabolomics/proteomics, including blood sampling for exploratory eptinezumab quantification, ADA biobanking and exploratory biomarkers, is covered by the main Informed Consent Form.
- t Sampling for pharmacogenetics is optional and covered by a separate Informed Consent Form.
- u Blood samples for safety ADA/NAb assessments and ADA biobanking (possible future analysis) will be drawn at Day 0/Visit 2, prior to the second eptinezumab infusion (Week 12/Visit 5), prior to the third eptinezumab infusion (Week 24/Visit 8), prior to the fourth eptinezumab infusion (Week 36/Visit 11), Completion Visit (Week 48/Visit 14), SFU Visit (Week 56/Visit 15). A Withdrawal Visit (if the participant withdraws) sample will only be drawn for the safety ADA/NAb assessments when applicable.
- v Participants must be monitored during the infusion and for a period of 1 hour from the end of infusion. Participants will be requested to stay longer should the investigator or designee determine this is clinically

warranted.

- w The eDiary closeout will take place at Completion Visit (Week 48/Visit 14) / Withdrawal Visit (for participants who withdraw). Details will be provided in a separate training module.
- x For women of childbearing potential, pregnancy test at the Screening Visit and the SFU Visit is to be conducted using serum beta-human chorionic gonadotropin (β -hCG). At all other visits, urine pregnancy testing will be performed and in case of a positive finding, further confirmatory testing will be performed via serum β -hCG.
- y Adverse events (serious and non-serious) must be collected, recorded, and reported to Lundbeck from the time the participant has signed the Informed Consent Form(s) at the Screening Visit. Pre-treatment adverse events will also be collected.
- z The Screening Visit assessments may be extended over several days if needed. The date of the first assessment (except Informed Consent Form) should be entered in the electronic case report form (eCRF) as the visit date. eDiary must be provided to the participant on the date of that first assessment, which is considered as the first day of the 28-day Screening Period.

